1.1 Background

Discovering how to clinically deliver conduction system pacing efficiently could be a paradigm shift. Early work on conduction system pacing focused on the His bundle, with right atrial mapping for the His signal and deployment of a lumenless pacing lead(1). Left bundle pacing (LBP) then emerged as an alternative, approaching via the basal right ventricular septum to deploy a lead through the septum to capture the left bundle on the left side of the septum(2,3)

Current literature report improved left ventricular function, heart failure outcomes and mortality in conduction system pacing(4,5). Additionally, LBP has a larger target area, can be done with low capture thresholds, has better threshold stability and large amplitude R waves(3). Widespread roll out of conduction system pacing clinically, however, faces three major challenges.

Challenge A1: Identifying target area for lead deployment

Despite growing adoption, conduction system pacing implants remains challenging. Even experienced device consultants take time to learn the technique. Experienced centres achieve implant success of 95%, but centres with new conduction system implanters (but highly experienced pacemaker implanters) have rates as low as 56%(6,7).

Fluoroscopic interpretation is challenging, for several reasons. The target area is smaller than conventional right ventricular pacing, and can be even smaller when there is fibrosis in the septum. The chambers may well be dilated, which displaces not only the fluoroscopic position of the target, but also its orientation. The lead can also be difficult to advance, because of septal fibrosis, unrecognised lead entanglement and unclear trans-septal trajectory. Interpretation of surface ECG and lead data is not straightforward either: there are many levels in the conduction system at which block can occur and it is difficult to distinguish them confidently. Lead entanglement and mal-orientation may be detectable with elaborate equipment such as intracardiac echocardiography (ICE) but we do not know what fluoroscopic or electrical features might provide routine clinical operators with a timely warning. Previous approaches to address these issues have involved normal-heart cadaveric studies which do not give the electrical context of a clinical implant(8).

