The CartoMerge module will be used to expedite anatomical mapping using the MRI data collected.

- 5. The mapping catheter will be removed and an intracardiac echo (ICE) catheter, will be inserted through the femoral vein.
- 6. The conduction system pacing lead will be inserted through the axillary vein. A right atrial lead will be inserted into the right ventricular apex for back up pacing in the instance the conduction system is bumped. The basal-septum, mid-septum, high-septum and anterior walls will be paced to identify electrical markers for optimal implant sites.
- 7. The lead will be visualised on the Carto maps created.
- 8. The lead will be deployed at the predetermined target site under direct visualisation using the ICE catheter. Through direct visualisation, three key determinants can be assessed:
 - 1. Lead trajectory through the septum with the goal of achieving perpendicularity
 - Lead septum interaction and whether there is evidence of entanglement preventing lead progression.
 - Relationship between the sheath and lead that can lead to or prevent failure of lead deployment.
- 9. Once the conduction lead is secured the right atrial lead will be pulled back and secured in the right atrium.
- 10. The procedure will be completed as per standard clinical implant protocol with routine clinical follow-up thereafter:

The information from echocardiography will be corroborated with the lead-septum interaction visualised on electro-anatomical maps created on CARTO.

In this cohort of patients, the conduction system lead will initially pace the His-bundle then the left bundle in order to collect data for both methods of physiological pacing. The information collected from ICE and electro-anatomical mapping will be used to develop a streamlined workflow that will map targeted areas, where challenging implant sites will be rapidly identified (such as areas of scar), reducing the number of attempted lead deployments and visualise lead-septum interaction, apposition and progression, improving safety parameters.

At the end of the procedure, the lead position will be documented with a very short, *single fluoroscopic acquisition*. This remains integral for future comparison in the instances of lead complications and in particular lead displacement.

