4.3 Control Arm

The control arm will consist of 25 patients undergoing a conduction system pacemaker using conventional pacing methods, with the same pacing indications as the study arm.

[figure not shown]

Figure 1: Recruitment workflow

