4.6 Study Outcome Measures

Primary Outcome Measures

1. Success rates of conduction system lead implant (fluoroless workflow vs conventional methods)

Secondary Outcome Measures

- Procedure and fluoroscopy times of the fluoroless workflow vs current conventional methods of His-bundle and Left-bundle pacing
- Procedure and fluoroscopy times of the fluoroless workflow vs conduction system implant to current right ventricular pacing
- 3. Assess capture threshold of His-bundle and Left-bundle pacing from the fluoroless workflow vs that of conventional methods of conduction system implantation
- 4. Number of times leads deployed in the fluoroless protocol vs conventional methods of conduction system implantation
- Complication rates in the fluoroless protocol vs conventional methods of conduction system implantation:

- a. Lead implanted at the incorrect position: non-septal positions
- b. Lead displacement
- c. Lead injury
- d. Rise in threshold (late complication)
- e. Vascular injury
- f. Perforation with or without subsequent tamponade
- g. Device related infection
- h. Pneumothorax

5 Participant Entry

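### Perforation without tamponade counts as a complication, but only the derivation cohort is documented as watched on ICE, so the item f comparison with controls mixes detection with harm

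*Protocol*

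**What the plan says.** Section 4.6 of the Protocol lists as a secondary outcome "Complication rates in the fluoroless protocol vs conventional methods of conduction system implantation". Two of its eight items matter here: item a, "Lead implanted at the incorrect position: non-septal positions", and item f, "Perforation with or without subsequent tamponade". Neither has a stated method or time of assessment.

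Imaging is described separately for each cohort:

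- **Derivation (4.1).** "The lead will be deployed at the predetermined target site under direct visualisation using the ICE catheter". Also, "The lead will be visualised on the Carto maps created". At the end of the procedure "the lead position will be documented with a very short" fluoroscopic acquisition, which 4.1 calls integral to later comparison if a lead complication, displacement above all, occurs.
- **Validation (4.2).** Mapping and the lead-septum pattern on CARTO are named. ICE and the final image are not mentioned.
- **Control (4.3).** "25 patients undergoing a conduction system pacemaker using conventional pacing methods". The control-group box, whose text falls within section 4.5, lists a 12-lead ECG and fluoroscopy during the procedure. The echocardiogram and MRI come before it.

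Section 4.4 gives all 75 patients the same visits. The complications it names are displacement, threshold rise, lead injury and infection. Perforation and malposition are not among them, although the list is worded as inclusive rather than complete.

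**The concern.** A perforation without tamponade may cause no symptoms, and whether it enters the count then depends on whether someone was looking with a tool that shows it. Item f admits such events by definition, and the looking is not the same in every cohort. An ICE-imaged patient and a control with the same silent injury could be recorded differently.

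Hypothesis 2 in section 1.2 (mapping makes implantation safer) and the section 2 objective on complication rates both draw on this comparison. Unequal detection does not shrink with more patients. It could also work against the sponsor, by hiding a real gain in safety. Part of it cannot be repaired at analysis, because an image not stored at implant cannot be recovered later.

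**Working it through.** **The plan's own figures.** Section 8 gives precision for implant time and success rate only. Both reproduce: 47.37/√25 = 9.47 minutes, and √(0.8 × 0.2/25) = 0.08. Neither concerns complications. Section 4.5 gives an added perforation risk of under 1 in 1000 each for ICE and for mapping. That is the risk of the research steps, not the rate of lead perforation or the chance of detecting it.

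**Means of detection set side by side.**

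| | Derivation | Validation | Control |
|---|---|---|---|
| ICE at deployment | yes (4.1) | not stated (4.2) | not listed |
| CARTO | yes (4.1) | yes (4.2) | not listed |
| Fluoroscopy | final acquisition (4.1) | not stated | during procedure |
| Stored end-of-procedure image | yes (4.1) | not stated | not stated (4.3) |
| Clinic visits | same (4.4) | same | same |

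The visits are the one row that is stated and identical throughout.

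**Item f.** Let p be the true rate and s the chance that an event is detected, with subscripts F for an ICE-imaged cohort and C for control.

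- Observed rate = p × s.
- Observed difference = p_F s_F − p_C s_C.
- If true rates are equal, this reduces to p(s_F − s_C). It is zero only if detection is equal, and n does not appear in it.

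**Scale.** One event in 25 is 1/25 = 4 percentage points.

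**Illustration under assumed values.** The Protocol supplies neither p nor s. The values below are assumptions chosen to show how the formula behaves, with the same true rate in both cohorts.

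| Assumed p | s_F | s_C | Observed F vs C | Difference | Expected events per 25 |
|---|---|---|---|---|---|
| 2% | 1.0 | 0.75 | 2.0% vs 1.5% | 0.5 points | 0.50 vs 0.38 |
| 4% | 1.0 | 0.75 | 4.0% vs 3.0% | 1.0 points | 1.00 vs 0.75 |
| 4% | 1.0 | 0.5 | 4.0% vs 2.0% | 2.0 points | 1.00 vs 0.50 |
| 4% | 0.9 | 0.3 | 3.6% vs 1.2% | 2.4 points | 0.90 vs 0.30 |

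The difference scales in proportion to p. At these rates it is less than one event per cohort.

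**Masking.** Suppose the true rate is 8% in controls and 4% with ICE, with detection 50% and 100%. Observed rates are 0.08 × 0.5 = 4% and 0.04 × 1.0 = 4%. A true halving then appears as no difference.

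**Random error for comparison.** With 0 events in 25, the one-sided 95% upper limit is 1 − 0.05^(1/25) = 11.3%.

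**Item a.** This item concerns where the lead ends up. A lead seen off the septum can be moved before it counts, so imaging may lower p_F as well as raise s_F. The sign of p_F s_F − p_C s_C is then undetermined.

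**The case against.** The case on the other side is substantial, and much of it limits the point.

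- **ICE is documented for derivation only.** A reader might infer that both fluoroless cohorts are better placed to show a silent perforation. The documents do not support that: 4.2 names CARTO only, and nothing says a CARTO map would reveal one. The asymmetry is least certain in the cohort that tests the workflow. The recruitment figure is not shown in the copy reviewed and may list more.
- **Controls are not assessed by fluoroscopy alone.** They have a 12-lead ECG during the procedure and the same visits as everyone else.
- **Section 1.1 does not call fluoroscopy insensitive to perforation.** Its remark, "Fluoroscopic interpretation is challenging, for several reasons", stands under the problem of finding the target area for deployment.
- **The Protocol does not say that ICE-only or CARTO-only observations count as complications.** True, but item f as worded would admit them, and nothing excludes them.
- **Section 8 names no test for complications**, so no formal inference rests on this contrast. The safety hypothesis still has to be read from it.
- **Ascertainment rules may sit in a SAP that is not shown.** That is fair for adjudication detail. It does not cover the scope of item f, which 4.6 fixes, or an image that must be taken at implant.
- **A fluoroscopic image is an imperfect standard for position.** That stands. Its merit here is that it can be the same in every cohort.

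**Conclusion.** The point holds for item f, most clearly for derivation against control. As written, the plan compares a rate that includes silent perforation between patients imaged on ICE at deployment and patients for whom only fluoroscopy and ECG are listed. The result cannot be read purely as harm.

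For item a, only the lack of a common method stands. A reader might infer a spurious excess of malposition in the fluoroless cohorts, but the documents do not support a direction, because live imaging may prevent the event as well as reveal it.

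The size is unknown. The documents give no rate of silent perforation and no detection probability, so any range of percentage points would be an assumption. What can be said is that one event moves a cohort's rate by 4 points, and that random error with 25 patients is itself large. The conclusion assumes that ICE can show a perforation that fluoroscopy and ECG may miss, and that such a finding would be recorded under item f. The point affects a few secondary items and leaves the primary outcome untouched, but the change is cheap and parts of it must be made before patients are implanted.

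**What to change.** 1. **Section 4.6, item f.** Make clinically manifest perforation or tamponade the compared event, identified by the same criteria and visits in all 75 patients. List perforations seen only on ICE or CARTO separately, by cohort, as description.
2. **Section 4.6, items a and b.** Judge final lead position and the baseline for displacement by one method in every cohort: the stored end-of-procedure fluoroscopic image plus the paced 12-lead ECG.
3. **Sections 4.2 and 4.3.** State that the documentation image in 4.1 applies there too.

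**Cost.** Wording, and one stored image per control in a procedure already done under fluoroscopy. Each validation patient has one very short acquisition, if that was not already intended. It counts towards fluoroscopy time, a compared outcome, as it does in derivation. Some true silent perforations leave the comparative rate and appear only descriptively.

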5.1 Pre-registration Evaluations

5.2 Inclusion Criteria

- Patients with a ventricular pacing indication: high grade atrioventricular block and symptomatic trifasicular, bifasicular block or left bundle branch block LBBB for cardiac resynchronisation therapy
- 2. Adults willing to take part (ages 18 100 years old)
- 3. Able to give consent.

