	9.3	CONFIDENTIALITY	
	9.4	INDEMNITY	
	9.5	Sponsor	
	9.6	Funding	
	9.7	Audits	
10		UDY MANAGEMENT	
11	L PUE	BLICATION POLICY	16
12	2 REF	FERENCES	17

CSP: Conduction system pacing CT: Computed tomography ECG: Electrocardiogram

EGG. Electrocardiogram
EGM: Electrogram
HBP: His-bundle pacing
ICE: Intracardiac echocardiogram
LBBB: Left bundle branch block LBP: Left bundle pacing
LBAP: Left bundle area pacing
LV: Left ventricle
LVAT: Left ventricular activation time

MRI: Magnetic resonance imaging

RV: Right ventricle

TOE: Transoesophageal echocardiogram TTE: Transthoracic echocardiogram

Study Summary

TITLE	Fluoroless Conduction System Implant		
DESIGN	Cohort observational study and interventional at validation phase		
AIMS	Define a feasible fluoroless protocol for conduction system lead implantation		
	Primary Outcomes:		
OUTCOME MEASURES	1. Success rate of conduction system lead implant Secondary Outcomes: 2. Fluoroscopy time 3. Total procedure time 4. Capture threshold 5. Number of times leads deployed 6. Complication rates: a. Lead implanted at the incorrect position: non-septal positions b. Lead displacement c. Lead injury d. Rise in threshold (late complication) e. Vascular injury f. Perforation with or without subsequent tamponade g. Device related infection h. Pneumothorax		

POPULATION	Patients with any indication for a pacemaker
ELIGIBILITY	Main Inclusion Criteria 1. Patients with a ventricular pacing indication: high grade atrioventricular block and symptomatic trifasicular or bifasicular block. (in order to assess the level of conduction system block) 2. Adults willing to take part (ages 18 – 100 years old) 3. Able to give consent.
	Main Exclusion Criteria 1. Unable to give consent 2. Children age < 18 years and adults > 100 years old 3. Pregnant patients 4. Pacing device in situ 5. Indication for cardiac resynchronisation therapy 5.
DURATION	1 year

1. Introduction

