1.3 Rational for Current Study

Currently conductions system pacing can have long fluoroscopy times when compared to conventional right ventricular pacing. This may be due to difficult cardiac anatomy, altered lead trajectory and obstacles such as entanglement, that is not readily visualised with fluoroscopy. As a result operators experience additional cumulative fluoroscopy times. Our study will devise a standardised implantation protocol using 3D electroanatomical mapping systems to reduce both fluoroscopy and procedure times.

2. Study Objectives

Primary Objective

The primary objective of this study is develop a fluoroless implant protocol of conduction system leads using 3D electroanatomical mapping.

Secondary Objective

The secondary objectives will be

- To reduce the overall procedure and fluoroscopy time with utilisation of targeted lead deployment.
- 2. Improve complication rates

3. Recruitment

A total of 75 patients will be recruited for the study

50 patients with a ventricular pacing indication (high grade atrioventricular block and symptomatic trifasicular or bifasicular block) for pacing will be recruited prospectively. The patients will be divided into two groups; 25 patients in the derivation cohort and 25 patients in the validation cohort. The derivation cohort will undergo a detailed research protocol to determine the optimised work flow and this will be applied prospectively to the validation cohort.

The success rates, procedure times, complication rates and fluoroscopy times will be assessed. The 25 patients undergoing conventional methods of conduction system pacing will be recruited as a control arm to compare these outcomes.

In summary, the 75 patients will be grouped as following; 25 patients in the derivation cohort, 25 patients in the validation cohort and 25 patients in the control arm.

4. Methodology

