4.1 Derivation

The derivation cohort will comprise of 25 prospectively recruited patients. These patients will undergo the research protocol. In these patients, we will attempt to implant a permanent conduction system pacing lead, in lieu of the RV or LV lead. The lead will be implanted by operators who have implanted more than 40 leads to overcome the learning curve.

Pre-implant

Prior to the procedure, patients will undergo a clinically indicated Cardiac MRI. We will use these scans to retrospectively assess for the presence of potential mechanisms which could prevent successful lead implantation, such as the presence of septal fibrosis and chamber dimensions, so that we can assess how these can contribute to challenges at the time of implant. We will also be able to review mechanisms for *successful* implants. This information will be corroborated with data collected from the electro-anatomical maps.

The MRI scans will also be used to merge the anatomical information using CartoMerge to reduce procedure times by building the anatomical geometry prior to the mapping-catheter collecting this information invasively.

During Implant

The participants will undergo the following procedural steps after written informed consent is gained:

- A left infraclavicular incision and axillary access for the lead will be gain as per standard clinical protocol.
- 2. Access from the femoral vein will be sought where a sheath will be placed in the femoral vein to introduce the mapping catheter.
- 3. Fast anatomical mapping (FAM) of the right atrial and right ventricular anatomy will be made where CartoMerge has not already created this anatomy. This will include the right ventricle, the tricuspid valve and the right ventricular outflow tract. Activation and voltage maps will be then be made of the His-bundle area (including the His cloud), right ventricle, right ventricular outflow tract and right ventricular septum.

This will help determine a few key aspects

- 1. Level of conduction system block and therefore guide site of lead deployment
- 2. Anatomy of the right heart and overcome challenges this may propose
- 3. Evidence of septal fibrosis and/or scar that need to be overcome
- 4. Activation pattern of the septum in conduction system block
- 4. Anatomical FAM maps, voltage maps and activation patterns will be compared against the data collected from the cardiac MRI to assess
 - 1. Accuracy of anatomy
 - 2. Fibrosis and scar patterns

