5.3 Exclusion Criteria

- 1. Unable to give consent
- Children age < 18 years and adults > 100 years old
- 3. Pregnant patients
 - As per standard of care, female patients of child-bearing age will have a urine pregnancy test prior to their procedure.

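### The Study Summary excludes patients with a CRT indication or a pacing device in situ; Section 5.2 includes LBBB for CRT, and Section 5.3 omits both exclusions

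*Protocol*

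**What the plan says.** Four places in the protocol describe who may enter.

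- **Study Summary, inclusion.** The qualifying indications are high-grade atrioventricular block and "symptomatic trifasicular or bifasicular block. (in order to assess the level of conduction system block". Left bundle branch block (LBBB) and CRT are not named.
- **Study Summary, main exclusions.** After consent, age and pregnancy, the list continues: "Pacing device in situ 5. Indication for cardiac resynchronisation therapy".
- **Section 3 (Recruitment).** The prospective derivation and validation patients are described as "50 patients with a ventricular pacing indication (high grade atrioventricular block and symptomatic trifasicular or bifasicular block". Again there is no LBBB or CRT.
- **Sections 5.2 and 5.3.** The inclusion list extends to "trifasicular, bifasicular block or left bundle branch block LBBB for cardiac resynchronisation therapy". The exclusion list has three items and closes with pregnancy, with a note that "female patients of child-bearing age will have a urine pregnancy test prior to their procedure". Neither a device in situ nor a CRT indication appears.

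Section 4.3 then defines the 25 controls as patients having conventional conduction system pacing "with the same pacing indications as the study arm".

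Two looser phrases bear on the population. The Summary's population row reads "Patients with any indication for a pacemaker", which is wider than either list. Section 4.1 says the conduction system lead is placed "in lieu of the RV or LV lead".

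**The concern.** Eligibility has to be settled in the protocol before patients are approached; an analysis plan cannot settle it afterwards. Here two screeners, each following the protocol faithfully, could make opposite decisions about the same patient, depending on whether they worked from the Summary or from Section 5.

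The design makes this more than an editorial matter. The primary outcome compares implant success between the fluoroless workflow and conventional methods, and the protocol describes no randomisation. Comparability therefore rests on who is admitted to each cohort. The workflow is also derived in one cohort and tested in another, so the two need the same entry rule. Section 1.1 itself names dilated chambers and septal fibrosis as reasons why implants are difficult, so on the protocol's own reasoning case mix can affect success and procedure time.

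**Working it through.** No figure in the protocol depends on this point. The precision figures in Section 8 reproduce and are untouched by it: 67/√2 = 47.38 and 47.38/√25 = 9.48 minutes (stated as 9.47), and √(0.8 × 0.2/25) = 0.08 (stated as 8%). The check is a comparison of text.

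**Step 1: set the lists side by side.**

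| Patient class | Study Summary | Section 3 | Sections 5.2 and 5.3 |
|---|---|---|---|
| High-grade AV block | included | included | included |
| Symptomatic bifascicular or trifascicular block | included | included | included |
| LBBB for CRT | excluded (CRT indication) | not listed | **included** |
| Pacing device in situ | excluded | not mentioned | **not excluded** |
| Unable to consent | excluded | not mentioned | excluded |
| Age under 18 or over 100 | excluded | not mentioned | excluded |
| Pregnant | excluded | not mentioned | excluded |

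**Step 2: count the exclusions.** The Summary has 5 (consent, age, pregnancy, device in situ, CRT indication). Section 5.3 has 3 (consent, age, pregnancy). 5 − 3 = 2 are missing, and 1 of those 2, the CRT indication, is an inclusion in Section 5.2.

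**Step 3: classify each disagreement.**
- *LBBB for CRT* is a direct contradiction: expressly in on one page, expressly out on another.
- *Device in situ* is an exclusion stated in one list and absent from the other. Section 5 does not invite such patients, but a patient who meets Section 5.2 and has a device would pass Section 5 and fail the Summary.

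**Step 4: see whether another passage settles it.** Section 3 agrees with the Summary on indications. The reference to an LV lead in Section 4.1 could fit a CRT population. The Summary's population row fits neither list. No passage gives one list precedence.

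**Step 5: follow it into the control arm.** Section 4.3 ties controls to the study arm's pacing indications, so the CRT conflict passes to the controls. Device status is not an indication, so that clause leaves it open.

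**Step 6: size.** Each cohort has 25 patients (3 × 25 = 75). One disputed patient is 1/25 = 4% of a cohort. The documents do not give the expected number of such patients or how their implant success differs, so this cannot be turned into a bias.

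**The case against.** The best case on the other side has four parts.

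1. *The device-in-situ point is an omission, not an opposite rule.* This is correct. Reading the lists together, one could apply the Summary's exclusion without contradicting Section 5.3. It is the weaker of the two points. It still needs correcting, because a list of main exclusions should not be stricter than the full list it summarises.

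2. *The text may carry remnants of tracked changes.* There is a stray deletion mark in Section 4.5, an empty extra item number at the end of the Summary's exclusions, and a doubled term for LBBB in Section 5.2. That is possible, but nothing in Sections 5.2 or 5.3 is marked as deleted, and neither list sits in an amendment log. Text lost from Section 5.3 could not explain an inclusion printed in Section 5.2. If this is the cause, the correction is the same.

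3. *The consequence is hypothetical.* If one list is used throughout, the between-arm difference is unaffected, and the control-arm clause works against an imbalance in indications. This stands as far as it goes: bias needs uneven application, and nothing shows that this would occur. What remains is that the population to which the results apply is undefined.

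4. *Section 5 can be read as already covering controls, and the loose phrases are not eligibility rules.* This is fair. Aligning those phrases is tidying and does not carry the finding.

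**Conclusion.** The concern holds, and the protocol should be corrected before it is used, or used further, for enrolment. Two patient classes are affected. For LBBB for CRT the protocol gives opposite instructions; for a device in situ, one list excludes and the other is silent. Two of the Summary's five exclusions are missing from Section 5.3.

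The conclusion rests only on the printed text and on both lists being current. No size of bias is claimed. If one list is applied uniformly, the effect is on who the results describe. If the lists are applied differently across the derivation, validation and control cohorts, case mix could differ in a comparison with no randomisation to protect it. The documents do not show which list is intended, and this review does not say which criterion is right.

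**What to change.** Reconcile the Study Summary, Section 3, Section 5.2 and Section 5.3 into a single eligibility list that applies to all three cohorts. State once, explicitly, whether a CRT indication is in or out, and the same for a device in situ; both decisions are the sponsor's. Have Section 4.3 refer to that full list instead of to pacing indications alone, so that device status is covered for controls too.

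Optionally, align the Summary's population row and the lead wording in Section 4.1 with the decision. If CRT patients stay in, a table of indication by cohort would let readers judge comparability.

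The cost is a protocol wording amendment, with no extra patients or procedures. The effect on the recruitment pool depends on which way the sponsor decides and cannot be stated from the documents.
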